transfused cells 24 hours after infusion. There was no regard for the RBC quality, longer-term *in vivo* survival kinetics, burden of RBC byproducts with repeated transfused doses, or tissue oxygenation capacity. Subsequent research has demonstrated that RBCs exhausted by refrigerated storage are structurally and functionally abnormal. These cells are more rigid, less tolerant of stress, form increased pathogenic *ex vivo* RBC-MPs, and abnormally adhere to the vascular endothelium.^{1,2,6,20} Intracellular ATP levels decrease during storage and can impair the ability of RBCs to effect local vasodilation in hypoxic microcirculatory environments to promote O₂ delivery.^{24,25} Furthermore, ATP losses decrease the function of vital intracellular ATP-dependent enzymes, such as the flippases that maintain normal membrane phospholipid asymmetry.²⁶ Stored RBCs are also depleted of 2,3-DPG and have lower p50, thus are less effectively able to transport and release O₂ where it is needed in the tissues.³ Once transfused, these altered RBCs are cleared from circulation and produce additional burdens of RBC byproducts and RBC-MPs already present in SCD patients.⁴⁻⁶ Rejuvenation of stored RBCs in the Blood Bank is a FDA-approved process that improves several cell parameters that are directly relevant to SCD pathophysiology, including RBC recovery, RBC-MP burden, *in vivo* RBC-MP formation, ATP and 2,3-DPG levels, p50, microcirculatory oxygenation, membrane deformability, and vascular endothelial adhesion.^{2,3,14-20} Surprisingly, benefits of RBC rejuvenation for transfusion in the SCD population specifically have not been explored. We postulate that RBC rejuvenation increases the *in vivo* survival of transfused RBCs, decreases pathogenic RBC-M formation *in vivo*, and can improve *in vivo* tissue oxygenation via normalization of p50.

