
assigned to manufacturer-defined windows derived from retention time of the peaks. The %Hb will be calculated by determining the area of a peak as a fraction of the total area of all Hb peaks on the HPLC chromatogram.

2: RBC-MP determinations. Samples will be whole blood in citrate. The first blood tube will be discarded to avoid contamination during venipuncture. Blood will be centrifuged at 1,500g for 10 min at 4 C. The supernatant will be carefully removed into microcentrifuge tubes, taking care not to disturb the buffy coat layer. A second centrifugation will be performed at 2,000g for 5 min to obtain platelet free plasma (PFP) to be frozen at -80 C. PFP aliquots (30 μ L) will be stained with the following markers/antibodies: 10 μ L FITC-labeled AnnexinV mixed 1:1 with Annexin binding buffer (10 mM HEPES, 140 mM NaCl, 2.5 mM CaCl2) and 2 μ L PE-labeled anti-CD235a. All markers/antibodies will be centrifuged at 20,000g x 20 min prior to use. RBCMs will be defined as Annexin+/CD235+ events. Calcium-free samples and

Rejuvesol® Washed RBC in Sickle Cell Patients Requiring Frequent Transfusions **Research Summary**

single-stained MP-free plasma samples (supernatant from normal, healthy donor PFP spun at 100,000g x 60min and stored at -80 C until use) will be used as negative controls. BD CompBeads® will be run as compensation controls per manufacturer's instructions. Stained samples will be incubated in the dark for 20 min and then further diluted with 500 μ L of Annexin binding buffer or phosphate buffered saline prior to analysis. All buffers will be filtered through a 0.1 μ m filter prior to use. CytoCount® beads will be added to each sample in equal volume as PFP (30 μ L) immediately prior to analysis to enable MP enumeration. The concentration of MPs in each sample will be calculated as follows: (MPs counted x concentration of beads) / number of beads counted. All samples will be analyzed on a Stratidigm S1000Ex (Stratidigm; San Jose, CA, USA) high-sensitivity flow cytometer equipped with a forward scatter photomultiplier tube (FSC PMT) using a side scatter (SSC) trigger and 0.1 μ m filtered sheath fluid. MP size gate for analysis will be set between 200 and 1000 nm utilizing Megamix Plus FSC/SSC® beads, which are a mixture of 900, 500, 300, 240, 200, 160 and 100 nm fluorescent beads. Event rates will be <8000 events/sec for all samples to minimize coincident events.

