RBC-mediated thrombin generation determinations. Phosphatidylserine (PS) has been found to directly correlate with rate of production of meizothrombin-antithrombin (mTAT) complexes and thrombin generation on RBCs. Whole blood samples will be collected in EDTA. For positive controls, washed RBCs will be diluted to 20% hematocrit in RBC wash buffer and incubated with 10mM N-ethylmaleimide (NEM) at 37 C for 30 min. NEM-treated cells will then be washed 3 times before incubation with a 4 μ M concentration of the calcium ionophore A23187 at 37 C for 30 min. Ionophore-treated cells will be washed 3 times and diluted to 2x10⁶ cells/mL in RBC wash buffer. Similar to controls, samples will be incubated and washed but without NEM or ionophore treatment. RBCs will be detected using PE-anti-glycophorin A (CD235a). RBC PS will be measured via binding of FITC-labeled Annexin V on a FACS Canto II flow cytometry (BD Biosciences Franklin Lakes, NJ).

RBC-MP-mediated thrombin generation determinations. Whole blood samples will be collected in citrate. PFP will be prepared as described above and frozen at -80 C. The Zymuphen ELISA (Aniara Inc., West Chester, OH) is a functional assay that measures the procoagulant activity of MPs in PFP. A microtiter plate is pre-coated with annexin V-streptavidin. PS+ MPs bind to the plate and expose their phospholipid surface, allowing

pro-thrombinase complex to cleave prothrombin into thrombin. Phospholipid in the sample is the limiting factor, so there is a direct relationship between MP phospholipid concentration and thrombin generation. Thrombin generation will be measured by a specific chromogenic substrate. Thawed PFP samples and kit controls will be diluted 1:20 in the kit sample diluent and supplemented with calcium, Factor Xa (FXa), and thrombin. A calibrator curve, diluted controls and diluted samples will be added to the ELISA plate and incubated for 1 hr at 37 C. The plate will be washed five times, then 100 μ L of Reagent 1 (FXa-FVa) and 50 μ L Reagent 2 (prothrombin) will be added and incubated for 10 min at 37 C, then 50 μ L of Reagent 3 (thrombin substrate) will be added, and incubated for 3 min at 37 C. Finally, 50 μ L of stop solution will be added and absorbance read at 405 nm. Results will be calculated from the calibrator curve.

3: O₂-binding curves and P50 determinations. RBCs will be washed and PBS

Rejuvesol® Washed RBC in Sickle Cell Patients Requiring Frequent Transfusions **Research Summary**

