1: To demonstrate that Rejuvenation improves *in vivo* RBC survival. We hypothesize that the loss of HbA over a transfusion interval will be reduced after a transfusion treatment with rejuvenated compared to standard RBCs. HbA/S determination is routinely performed pre- and post- treatments. The %HbA decrement is the current pre-treatment HbA – previous post treatment HbA in %. Our primary outcome variable will be HbA decrement per day to account for minor variability. A generalized linear model will be applied to determine whether the mean difference in HbA exceeds +/-19%. Secondary outcomes will evaluate actual HbA decrement (g/dl) with and without indexing to calculated circulating blood volume. If %HbA decrement with rejuvenated units exceeds -19% we will reject the null hypothesis and conclude that rejuvenation will permit prolonging transfusion intervals by a week to maintain the same %HbA target. Whether or not we reject the null hypothesis, these data will inform treatment effect size and prospective collection of %HbA variability can validate preliminary data strengthening future sample size estimate calculations.

2: To determine whether Rejuvenation reduces *in vivo*, RBC microparticles. We hypothesize that *in vivo* RBC-MP counts and RBC/RBC-MP-mediated thrombin generation before transfusion therapy will be lower after a prior treatment with rejuvenated compared to standard RBCs (“trough level”). Similarly, RBC-MP counts and RBC/RBC-MP-mediated thrombin generation will be lower immediately after transfusion therapy with rejuvenated compared to standard RBCs (“peak level”). These secondary outcomes will inform on effect size of rejuvenation on the immediate changes in RBC-MP counts after treatment. If reduction in RBC-MPs is augmented by rejuvenation, better efficacy of treatment could be postulated and subsequently tested, as this will minimize the contribution of transfusion therapy to the

preexisting, prothrombotic MP burden. Phosphatidylserine (PS) has been found to directly correlate with rate of production of meizothrombin-antithrombin (mTAT) complexes and thrombin generation on RBCs. The capacity of RBCs and RBC-MPs to generate thrombin could inform evaluation of future anticoagulation needs and targets. Wilcoxon Rank Sum tests will be used to compare RBC-MP counts and thrombin generation.

3: To demonstrate optimal *in vivo* O2 delivery capacity after Rejuvenation. We

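### The only RBC microparticle count requires annexin V binding, so a fall cannot be told apart from less exposed phosphatidylserine on the same number of particles

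*Combined protocol and SAP*

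**What the plan says.** Objective 2, in the Purpose of the Study and again in Data Analysis & Statistical Considerations, asks whether rejuvenation reduces RBC microparticles in vivo. RBC-MP counts and thrombin generation are compared between products before transfusion (trough) and just after it (peak). The objective's wording puts no PS qualifier on the counts.

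The three measures are defined under Specific procedures, item 2:

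- **Flow count.** Platelet-free plasma is stained with annexin V, which marks exposed PS, and with "PE-labeled anti-CD235a", which marks red-cell origin. The counting rule is "RBCMs will be defined as Annexin+/CD235+ events", within a 200-1000 nm size gate and scaled by counting beads.
- **RBC-mediated thrombin generation.** "RBC PS will be measured via binding of FITC-labeled Annexin V on a FACS Canto II flow cytometry".
- **RBC-MP-mediated thrombin generation.** In the ELISA, "A microtiter plate is pre-coated with annexin V-streptavidin" and "PS+ MPs bind to the plate and expose their phospholipid surface".

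Background & Significance says that ATP loss impairs ATP-dependent enzymes "such as the flippases that maintain normal membrane phospholipid asymmetry", and lists ATP among the cell parameters that rejuvenation improves. The analysis section draws this inference: "If reduction in RBC-MPs is augmented by rejuvenation, better efficacy of treatment could be postulated and subsequently tested". It gives the reason as a smaller contribution of transfusion to the prothrombotic particle load. No total CD235a+ count and no PS-positive fraction is planned.

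**The concern.** A count meant to show how many red-cell particles are present should not depend on a property that the treatment may itself alter. Here it does. CD235a establishes that a particle came from a red cell; the annexin V requirement adds a second condition, exposed PS. By the plan's own account of ATP and phospholipid asymmetry, rejuvenation could act on that second condition.

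Background & Significance postulates less microparticle formation in vivo. A fall in the double-positive count is compatible with that, but equally with unchanged formation and less exposed PS. These are different findings for the larger study that the pilot is meant to inform: one concerns how many particles are shed, the other how procoagulant they are. The plan collects the material to separate them but does not report it.

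**Working it through.** The documents give no effect size or PS-positive fraction for objective 2, so there is no figure to reproduce. The check has two parts.

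**1. Does any planned measure give particle number independently of PS?**

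- The flow count does not, because an annexin-negative CD235a+ event is dropped and the bead formula has no term for it.
- The RBC assay does not, because it reads annexin V binding on intact red cells, not on particles.
- The ELISA does not, because it captures only PS-positive particles before the thrombin step. As described, it also has no red-cell selection.

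**2. What happens to the count if only PS exposure changes?**

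Let N be all CD235a+ particles in the size gate and f the fraction that is annexin V positive. Then

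count = N × f

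and, with N equal after both products, the apparent relative change is f_R / f_S − 1, where S is standard and R is rejuvenated.

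The fractions below are **assumptions**: f_S of 50% to 80%, falling by 10 to 20 percentage points.

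| f_S | f_R | f_R / f_S − 1 | True change in N |
|---|---|---|---|
| 0.80 | 0.70 | −12.5% | 0 |
| 0.80 | 0.60 | −25% | 0 |
| 0.50 | 0.40 | −20% | 0 |
| 0.50 | 0.30 | −40% | 0 |

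The relative fall is the drop divided by the starting fraction, so the extremes under these assumptions are 10/80 = 12.5% and 20/50 = 40%.

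The ambiguity can be seen from a standard-product value of N = 1000 and f = 0.80, which gives a count of 800. Two different effects of rejuvenation then give the same result:

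- less exposed PS: 1000 × 0.60 = 600;
- fewer particles: 750 × 0.80 = 600.

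Both would appear as 800 to 600, a 25% fall. The total CD235a+ count separates them (1000 against 750), as does the PS-positive fraction (0.60 against 0.80).

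This is an identity. It shows what the count cannot distinguish; it is not evidence that PS on shed particles does change.

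**The case against.** The strongest reply is that PS-positive particles are the right target. The stated purpose concerns prothrombotic microparticles, the reason given for objective 2 is the prothrombotic particle load, and the assay text links PS to thrombin generation. For that aim, a fall in PS-positive particles is a meaningful result even if PS-negative ones remain. This stands: the endpoint is legitimate and should be kept. What it does not cover is the unqualified wording of the objective and the postulate about particle formation.

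The mechanism is also an extrapolation. The background text describes enzymes inside cells. Nothing in the documents shows that rejuvenation changes the PS-positive fraction of shed particles in patient plasma, which also holds the patient's own particles. The same section lists lower microparticle burden and formation among the effects of rejuvenation, so a true fall in number is just as consistent with the plan. This stands too, and limits the point to an ambiguity.

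A reader might infer that the plan would present three agreeing annexin-based results as independent proof of fewer particles. The documents do not support that: the other two assays are labelled thrombin generation, counts and thrombin generation are listed as separate outcomes, and nowhere is one used to confirm the other.

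Finally, this is a secondary outcome in a pilot of 4 patients, and annexin-negative events could be gated later if the files are kept. That lowers the stakes, but a count whose meaning is settled in advance is worth more for planning than one reinterpreted afterwards.

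**Conclusion.** The point holds as an ambiguity of measurement. The planned RBC-MP count cannot separate fewer red-cell particles from less exposed PS, and no other planned measure resolves it. Under the assumed fractions (50-80%, falling 10-20 points, particle number unchanged) the count would fall by 12.5% to 40%. The true size is unknown because the documents give no PS-positive fraction.

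Two stronger conclusions are tempting, and neither is supported. One is that the count is biased in favour of rejuvenation; that would need evidence of an effect on the PS of shed particles, which the documents do not contain. The other is that the total CD235a+ count alone should decide objective 2; the objective is framed around prothrombotic load, and a measure that ignores PS should not override it.

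**What to change.** In Specific procedures, item 2 (RBC-MP determinations):

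- keep Annexin+/CD235a+ events as the prothrombotic endpoint, but name it PS-positive RBC-MPs;
- from the same acquisition, also report all CD235a+ events in the 200-1000 nm gate, whatever their annexin signal, using the same bead formula;
- report the PS-positive fraction, that is, the first divided by the second.

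In Data Analysis & Statistical Considerations, objective 2, analyse these at trough and at peak. State in advance that if the PS-positive count falls and the total CD235a+ count does not, the result will be described as lower PS exposure or lower procoagulant potential, not as fewer microparticles formed.

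The cost is small. Anti-CD235a is already in the tube and acquisition is triggered on side scatter, not on annexin, so annexin-negative events above that threshold are already acquired. No extra blood or reagent is needed. The downside is one more secondary result and a single-marker gate likely to carry more background. That background should be judged against the MP-free plasma negative controls already planned; the plan gives no procedure for subtracting it, so how the controls will be used should be written down.

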Privacy, Data Storage & Confidentiality – Study records that identify subjects will be kept confidential as required by law. Federal Privacy Regulations provide safeguards for privacy, security, and authorized access. Except when required by law, the subjects will

not be identified by name, social security number, address, telephone number, or any other direct personal identifier in study records disclosed outside of Duke University Health System (DUHS). For records disclosed outside of DUHS, subjects will be assigned a unique code number. The key to the code will be kept in a locked file in [name] office. The study results will be retained in the subject's research record for a minimum of 6 years. Any research information in the medical record will also be kept indefinitely. Some information collected about subjects only for this research study may

Rejuvesol® Washed RBC in Sickle Cell Patients Requiring Frequent Transfusions
Research Summary

be kept in a research study record separate from subject's medical record, and some research information may also be part of the subject's medical record. Subjects will not have access to this research information until the end of the study.

Rejuvesol® Washed RBC in Sickle Cell Patients Requiring Frequent Transfusions **Research Summary**

References-

